19.8.2 Premature Discontinuation Due to Lack of Efficacy or Adverse Events

The distribution of patients who prematurely discontinue due to lack of efficacy or adverse events will be summarized. Patients who prematurely discontinue after having been followed in the Observation Period only will be also be summarized.

19.9 SAFETY ANALYSES

19.9.1 Safety Population

The Safety Population will consist of all patients who have received a single dose of study medication, i.e., this same population will be used both for the efficacy and safety evaluations. The Safety Population will be used in all safety analyses.

19.9.2 Adverse Events

All treatment emergent AEs (TEAE) will be summarized overall and for each body system and preferred term by treatment group, relationship to study medication, and severity. For tabulations by severity, only a patient's most severe event within the category (e.g., overall, body system, or preferred term) will be counted. Adverse events will be dichotomized into "related" (probably and possibly) and "unrelated" (unlikely). "Treatment-emergent" will be defined as starting or worsening after the first dose of study drug. If the start date is missing, the event is assumed to be treatment emergent. All SAEs will be tabulated as well.

Although nalbuphine is not a controlled substance in the United States, adverse events of special interest that suggest a possible addiction or abuse potential or withdrawal will be specifically analyzed to screen for these effects. The list of MedDRA preferred terms for adverse events of special interest will be described in the Statistical Analysis Plan.

19.9.3 Vital Signs

Vital signs, including BP, HR, body temperature, and RR, and weight will be summarized by treatment group at Baseline and at each assessment time point during the post dosing period.

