- review of concomitant medications, including over-the-counter medications, nutritional supplements, and vitamins; also collect the TR03 rescue medication log
- retrieve any remaining study drug from the parent study TR03
- administer the Worst itch NRS (paper version) and **review score for eligibility to either enter the Treatment Period or to continue in screening under the Observation Period**
 - a) If the Worst Itch NRS score is < 5 , start the Observation Period. Do NOT initiate study drug treatment at this visit
 - b) If Worst Itch NRS score is ≥ 5 , confirm eligibility and start the Treatment Period (see below, ‘For patients qualifying for drug Treatment Period only’).

The Worst Itch NRS (paper version) must be administered at the study site under the supervision of and by trained study staff, strictly adhering to PRO Administration Instructions (see Study Reference Manual)

For patients qualifying for the drug Treatment Period only (Visit 1a is also study visit TV1):

- complete PAS
- administer PRO measurements (paper versions):
 - Average itch intensity NRS
 - VRS
 - ItchyQoL
 - MOS Sleep-R
 - HADS
 - PBI-P

The PRO questionnaires must be administered at the study site under the supervision of and by trained study staff, strictly adhering to PRO Administration Instructions (see Study Reference Manual)

- perform skin biopsy (optional procedure at select sites only). Obtain 3 samples (i.e., H&E, nerve fiber density (histology) and MOR/KOR density (histology, Western Blot)); see the Lab and Study Reference Manuals for details
- dispense enough Study Drug to the patient for required dosing until their return at Treatment Visit 2, TV2
- dispense the Dosing Diary and instruct the patient on how to complete it
- dispense the TR03ext Rescue Medication Log and instruct the patient on how to complete it

- instruct patients to self-administer the first dose on the evening of Visit 1a at home
- instruct patients to notify the Investigator if any significant CNS AEs occur, and not to drive or operate dangerous machinery until the effect of the Study Drug can be assessed by the Investigator, see [Section 9.3](#)
- instruct the patient to take the Study Drug twice daily at approximately the same times of day. All patients should be instructed to titrate to their most tolerated dose. See [Table 3](#) Drug Dosing Schedule for more information. Here is the recommended Week 1 titration schedule for patients who tolerate study drug:

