9.6.8 Unscheduled Visits

If a patient needs to be evaluated in relation to the study on a day other than one of the study visit days, that day will be considered an Unscheduled Visit. The reason for each unscheduled visit will be recorded and the following procedures will be performed: vital signs (BP, HR, RR, temperature), assessment for AEs, review of concomitant medications (including rescue medications), and Study Drug accountability. Additional procedures such as central or local laboratory sample collection may also take place, if clinically indicated. See [Section 17.5.2.1](#) in regards to the handling of positive pregnancy test results. All unscheduled visits will be recorded on the Unscheduled Visit CRF.

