9.7.8 Safety Assessments

As summarized in Section 6.2.7 of the Investigator's Brochure, the CNS has been identified as the only target organ when nalbuphine was given to animals at high doses. In addition, the most frequently reported adverse events reported in the nalbuphine HCl ER tablet dosing studies were primarily in the nervous system and gastrointestinal organ system categories. In order to monitor any potential CNS related side effects, a brief neurological assessment will be conducted at each study visit as well as a focused neurological medical history will be obtained at screening.

Safety will be determined by evaluation of the following:

- AEs
- Vital signs including weight, BP, heart rate (HR), respiratory rate (RR), and body temperature
- Physical examination
- Clinical laboratory data (see [Appendix 3](#) for list of analytes)
- Investigator reviewed ECG and central cardiac core laboratory read 12 Lead-ECG, cardiovascular grading, and/or cardiovascular related prohibited medications
- Subjective Opiate Withdrawal Scale (SOWS)

The SOWS is a self-administered scale for grading opioid withdrawal symptoms. It contains 16 symptoms whose intensity the patient rates on a scale of 0 ("not at all") to 4 ("extremely"). The instrument can be found in [Appendix 4](#). In this study, patients will complete SOWS daily, starting at TV14, End of Treatment Visit through to the Washout and Safety Follow-up Period Visit. The SOWS will also be completed at the Premature Discontinue of Study Drug Treatment Visit. As with all patients who are discontinued from study drug, the patient will complete a daily SOWS scale for the two weeks following the last dose of study drug (unless consent is withdrawn). The SOWS is a self-administered scale for grading opioid withdrawal symptoms. If the patient is experiencing any symptoms on the SOW scale to a moderate degree, they will be instructed to contact the site. If a patient is determined to be experiencing significant subjective withdrawal symptoms (at the Investigator's discretion), they will be offered treatment.

The following will be used to assess patient eligibility to continue participation if the patient experiences CHF, angina pectoris and/or other cardiovascular exclusion criteria (see [Section 8.3](#) for the Exclusion Criteria and [Appendix 5](#) for the grading scales)

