17.2 VITAL SIGN MEASUREMENTS

Blood pressure and HR will be taken while sitting or semi-recumbent/recumbent for at least 5 minutes. Temperature may be taken by any standard method (e.g., oral, tympanic, rectal, etc.), but the method must be recorded.

Vital signs (BP, HR, RR, body temperature, and weight) will be obtained according to the Schedule of Events ([Appendix 1](#)). The height, weight and BMI will be recorded only on Visit 1a.

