Appendix 1: Schedule of Events

Table 4: Schedule of Events for Visits 1a and 1b (Day 1 of Week 1 of Treatment Period)		
Visit	1a¹	1b⁴
Informed Consent ²	X	
Confirm Eligibility	X	
Vital Signs ³	X	X
Physical Examination	X	X
Neurological Exam	X	X
Central Clinical Labs ⁵ & serum Pregnancy Test ⁶	X	X
Urinalysis	X	X
Urine for pregnancy test ¹¹	X	X
Blood for PK	X	X
Perform skin biopsy (only at select sites and the procedure is optional) ⁹	X	X
12-lead ECG ¹²	X	X
Worst itch Numerical Rating Scale (NRS) ⁷	X	X
Average itch intensity Numerical Rating Scale (NRS) ⁷	X ⁹	X
Verbal Rating Scale (VRS) ⁷	X ⁹	X
ItchyQoL ⁷	X ⁹	X
MOS Sleep-R ⁷	X ⁹	X
Hospital Anxiety and Depression Scales (HADS) ⁷	X ⁹	X
Patient Benefit Index Pruritus (PBI-P) ⁷	X ⁹	X
Prurigo Activity Score (PAS)	X ⁹	X
Record AEs	X	X
Review Rescue Medications and Concomitant Medications	X ⁸	X
Retrieve TR03 study drug	X	
Dispense Study Drug for TR03ext ¹³	X ⁹	X
Collect Rescue Medication Log for TR03	X	
First dose of Study Drug for TR03ext ^{10,13}	X ⁹	X
Dispense Drug Dosing Instructions and Dosing Diary	X	X
Dispense TR03ext Rescue Medication Log	X	X

¹Visit 6/1a procedures in common do not have to be repeated if visits are performed on the same day.

²To be completed any time before start of Visit 1a procedures

³BP and HR (sitting or semi-recumbent), RR, temperature. Height, weight, and BMI at Visit 1a only.

⁴Visit 1b is the first visit of the Treatment Period for patients transitioning from the Observation Period to the Treatment Period.

⁵Hematology and chemistry

⁶Females of Childbearing potential only

⁷Questionnaires must be administered strictly adhering to instructions (see Study Reference Manual)

⁸Includes review of patient TR03 Rescue Medication Log

⁹Study procedures only conducted if patient qualifies to enter the Treatment Period based on Worst itch NRS ≥ 5

¹⁰Titrate study drug according to the schedule in [Table 3](#);

The first dose of study drug treatment will define enrollment into the study

¹¹For female patients of child-bearing potential, a urine pregnancy test must be negative prior to dispensing study drug.

¹²ECGs are to be performed after the patient has been in the supine position for at least 5 minutes. ECGs will be read by the Investigators for clinical significance and centrally by a core ECG laboratory for analytical and DSMB safety review

¹³The first dose of study drug is to be taken in the evening, see [Section 9.7.1](#) and [Section 9.3](#)

Table 5: Treatment Weeks 2-4

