Average itch intensity NRS ⁷	X	X	X	X	X	X	X	X	X	X	X	X	X		X
ItchyQoL	X	X	X	X	X	X	X	X	X	X	X	X	X		X
VRS ⁷	X	X	X	X	X	X	X	X	X	X	X	X	X		X
MOS Sleep-R ⁷	X	X	X	X	X	X	X	X	X	X	X	X	X		X
HADS ⁷	X	X	X	X	X	X	X	X	X	X	X	X	X		X
SOWS ⁷												X			X
Dispense 14 day SOWS packet ¹⁵												X			
Retrieve 14 day SOWS packet ¹⁵													X		
Record AEs	X	X	X	X	X	X	X	X	X	X	X	X	X	X	X
Record Concomitant Medications ¹⁶	X	X	X	X	X	X	X	X	X	X	X	X	X	X	X
Reinforce Compliance	X	X	X	X	X	X	X	X	X	X	X				
Study Drug Accountability	X	X	X	X	X	X ⁸	X	X	X	X	X	X			X ⁸
Study Drug BID	X	X	X	X	X	X	X	X	X	X	X				

¹Patients who were previously in the Observation Period should start the Treatment Period at Visit 1b and continue in the study for 38-46 weeks; the total number of weeks in the combined Observation and Treatment Periods is no more than 50 weeks. The last scheduled visit on study drug for patients previously in the Observation Period should be TV 14 regardless of the study week.

² The number of Treatment Weeks prior to TV 14 will vary for patients who prematurely discontinue study drug for reasons other than withdrawal of consent see [Section 11](#).

³Two allowable dose reductions are permitted during Treatment Weeks 5 – 50 (a patient can be reduced to 30 mg BID). If a third dose reduction is needed, the patient should be discontinued from the study.

⁴ BP and HR (sitting or semi-recumbent), RR, temperature

⁵For female patients of child-bearing potential, a urine pregnancy test must be negative prior to dispensing additional study drug.

⁶Hematology and chemistry.

⁷Questionnaires must be administered strictly adhering to instructions (see Study Reference Manual)

⁸Retrieve remaining study drug at TV 14 or ET Visit

⁹ET Visit is conducted within 2 weeks of study drug termination, see [Section 12](#)

¹⁰Skin biopsy material for nerve fiber density, histology (H&E) and MOR/KOR density to be performed, only at select sites (optional procedure)

¹¹Females of Childbearing potential only

¹²Visit windows will be +/-3 Days

¹³ECGs are to be performed after the patient has been in the supine position for at least 5 minutes. ECGs will be read by the Investigators for clinical significance and centrally by a core ECG laboratory for analytical and DSMB safety review

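### Weight is planned for a post-dose safety summary, but the schedule collects it only at pre-dose Visit 1a, so that summary would have no data

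*Protocol*

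**What the plan says.** Two sections treat weight as a safety measure to be followed over time.

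- Section 9.7.8 lists what safety will be judged on, including "Vital signs including weight, BP, heart rate (HR), respiratory rate (RR), and body temperature".
- Section 19.9.3 has one sentence for all vital signs. It names blood pressure, heart rate, temperature and respiratory rate, and closes with "weight will be summarized by treatment group at Baseline and at each assessment time point during the post dosing period".

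The sections that tell sites what to do say something else.

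- Section 17.2 opens with "Vital signs (BP, HR, RR, body temperature, and weight) will be obtained according to the Schedule of Events" and then limits it: "The height, weight and BMI will be recorded only on Visit 1a".
- Footnote 3 of Table 4 (Visits 1a and 1b) agrees with that limit: "Height, weight, and BMI at Visit 1a only".
- The vital-sign footnotes of Table 5 (TV2), Table 6 (TV3 to TV14, Washout and Early Termination) and Table 7 (Observation Visits) define vital signs as "BP and HR (sitting or semi-recumbent), RR, temperature".
- Section 9.6.8, for unscheduled visits, asks for "vital signs (BP, HR, RR, temperature), assessment for AEs", again without weight.

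Visit 1a comes before any study drug in this trial. Section 9.6.1 tells the site to "instruct patients to self-administer the first dose on the evening of Visit 1a at home".

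**The concern.** The analysis section promises a summary that the collection schedule cannot supply. This cannot be left to the statistical analysis plan, because an analysis plan cannot summarize measurements that sites were told not to take, and a missed weight cannot be recovered afterwards.

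What is at stake is one listed safety variable in a study whose primary objective is safety and tolerability over up to 50 weeks of treatment. As the text stands, a site that follows the schedule never weighs a patient after the first dose. A site that follows the general wording of Sections 9.7.8 and 17.2 might do so. Any post-dose weights that did reach the database would then depend on how each site read the protocol. They could not be summarized as a planned assessment of the whole safety population.

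A second, smaller gap concerns patients who come through the Observation Period. They are not weighed at Visit 1b, when they start treatment, so their only weight dates from before that period.

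**Working it through.** The plan gives no figure to reproduce. The check is a count of visits, with the vital-sign footnotes read visit by visit.

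**Where weight is scheduled**

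| Visit | Source | Weight? |
|---|---|---|
| Visit 1a (pre-dose) | Table 4, footnote 3; Section 17.2 | Yes |
| OV2 to OV4 (pre-dose) | Table 7, footnote 3 | No |
| Visit 1b (pre-dose) | Table 4, footnote 3 | No |
| TV2 | Table 5, footnote 3 | No |
| TV3 to TV14, Washout | Table 6, footnote 4 | No |
| Early Termination | Table 6, footnote 4 | No |
| Unscheduled | Section 9.6.8 | No |

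**Number of on-site post-dose visits for a completer**

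Tables 5 and 6 give the full series. Table 8 gives the last treatment visit before TV14 for those who enter through Visit 1b.

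- Entry at Visit 1a: TV2 to TV13 is 12 visits; adding TV14 and Washout gives 12 + 2 = 14.
- Entry from OV2: TV2 to TV13 is 12 visits; 12 + 2 = 14.
- Entry from OV3: TV2 to TV12 is 11 visits; 11 + 2 = 13.
- Entry from OV4: TV2 to TV11 is 10 visits; 10 + 2 = 12.

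The number of these with a scheduled weight is 0 in every row. Patients who stop early have fewer visits and also 0 weights.

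**Age of the only weight at first dose**

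- Entry at Visit 1a: same day, since the first dose is taken that evening.
- Entry through Visit 1b: Table 7 places OV2, OV3 and OV4 at weeks 4, 8 and 12, each within 3 days either way. The Visit 1a weight is therefore about 4, 8 or 12 weeks old at first dose.

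**Sensitivity to the text used**

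The file contains a second copy of Table 4, whose footnote 3 includes weight for both Visit 1a and Visit 1b. Visit 1b is also pre-dose, so under that copy the post-dose count is still 0; only the gap at Visit 1b would close.

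**The case against.** The best case for the plan has four parts.

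*The sentence in Section 19.9.3 is generic.* It covers all vital signs together and does not promise a separate weight table. Its reference to each assessment time point could be read, for weight, as whenever weight happens to be assessed. That reading is possible, but it leaves the post-dosing half of the sentence with no content for weight, although the sentence names weight expressly.

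*Section 17.2 can be read without contradiction.* A general rule pointing to the schedule is followed by a specific limit, and the schedule repeats the limit. This is fair as far as Section 17.2 and Table 4 go. It also suggests that the limit was intended and that the mention in Section 19.9.3 may be a leftover. It does not reconcile either of them with Section 19.9.3, and it supports deletion as a legitimate alternative remedy.

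*Sites may weigh patients anyway.* The visit-by-visit instructions only say to obtain vital signs. But the word only in Section 17.2 and every post-dose footnote point the other way, and uneven collection would be no better.

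*The safety consequence is limited.* This stands. A reader might infer that the primary safety objective is compromised because weight would reveal a slow, cumulative effect of nausea, vomiting and constipation. The protocol does not support that. Section 9.3 says such gastrointestinal effects occur early and can limit treatment; it does not describe a slow build-up. No section names weight change as a risk. The primary endpoint in Section 5.1 is treatment-emergent adverse events. Adverse events are recorded at every treatment visit, and clinically significant worsening at a physical examination is reported as an adverse event (Section 17.1). An important weight change therefore has a route into the data even without a scheduled measurement.

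A reader might also infer that Visit 1b entrants have no valid weight baseline. Section 5.2 makes Visit 1b the baseline for efficacy endpoints and says nothing of vital signs, and the Visit 1a weight is pre-dose for both entry routes. The accurate statement is that their only weight is older, not that it is invalid.

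**Conclusion.** The inconsistency is real. Sections 9.7.8 and 19.9.3 call for weight as a safety measure summarized after dosing. Section 17.2, Table 4 footnote 3 and the footnotes of Tables 5 to 7 together schedule it at 0 of 14, 13 or 12 post-dose visits, depending on entry route, and not at Early Termination. The post-dose weight summary would have no planned data.

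This assumes that sites follow the schedule footnotes and the explicit limit in Section 17.2. The denominators apply to completers.

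The point is worth correcting but should not be ranked higher than that: it affects one supporting safety variable and leaves the primary endpoint and the adverse-event analyses as they are.

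**What to change.** Reconcile Sections 9.7.8, 17.2 and 19.9.3 with Tables 4 to 6.

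**Preferred.** In Section 17.2 and Table 4 footnote 3, let the Visit 1a limit apply to height and BMI alone. Add weight at Visit 1b (Table 4) and at TV8, TV14 and Early Termination (Table 6). Vital signs and a physical examination are already scheduled at all four, so no visit is added. Every completer, including those from OV4, passes through TV8 and TV14. Section 11 asks patients who stop drug early for reasons other than withdrawal of consent to complete TV14, and Section 9.6.7 asks those who withdraw consent to attend Early Termination if feasible. Nearly every treated patient would then have a weight at the start of treatment and at least one after it.

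State in Section 19.9.3 that weight is summarized at those visits only.

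The cost is a protocol amendment, with ethics committee submission and approval where required (Section 20.1), and a few data fields. A completer gains two weighings (TV8, TV14), or three if entering through Visit 1b. With the stated ceiling of about 60 patients, that is at most about 60 × 3 = 180 weighings among completers.

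**Alternative.** If the sponsor does not want post-dose weight, remove it from the safety measures in Section 9.7.8 and from the post-dosing summary in Section 19.9.3, and report the Visit 1a value as a baseline characteristic. This needs no new data, but gives up any scheduled measure of weight change on treatment.

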19.9.4 Laboratory Evaluations

Clinical safety laboratory data will be summarized descriptively by treatment group at baseline and at each scheduled visit. Summaries of safety laboratory parameters will include the first measurement of each scheduled assessment but repeat assessments done at the same study time point will not be included in summary calculations. Lab data will also be listed by treatment, patient, and visit. Listings will include scheduled, unscheduled, and repeat evaluations. A listing of markedly abnormal values, as defined in the Statistical Analysis Plan, will additionally be generated.

19.9.5 Physical Examinations

Abnormal physical examination findings that suggest a clinically significant worsening will be reported as AEs and analyzed as such. Clinically significant findings noted prior to start of Study Drug treatment will be recorded as medical history and analyzed as such.

19.9.6 Electrocardiograms

A standard 12-lead ECG will be obtained on Visit 1a/1b (pre-treatment) and subsequently, according to the Schedule of Events in [Appendix 1](#). Electrocardiogram intervals (PR, RR, and QTcF) will be summarized with descriptive statistics. All findings, including any follow-up ECGs as a result of any significant abnormal results, will be listed by treatment, patient, and visit.

ECG procedures should be automatically repeated if the following results are obtained: artifact, excessive noise, reversed leads, or baseline wander. Repeating ECG procedures for any other reason will require prior written approval from the Sponsor.

19.10 DETERMINATION OF SAMPLE SIZE

As this is a safety extension study for which patients will be recruited from patients who have completed parent study TR03, the sample size cannot be predicted. No formal sample size calculations have been performed and no inferential statistics are planned. The maximum number of patients will not exceed the number of patients who completed TR03 (i.e., approximately 60 patients).

19.11 PHARMACOKINETIC AND PHARMACOKINETIC / PHARMACODYNAMIC ANALYSES

The Study Drug plasma concentration data will be provided as data listings and will be summarized descriptively (mean, median, SD, minimum, and maximum) by collection time and nalbuphine dose. Additionally, these PK data may be analyzed through population, nonlinear mixed effects modeling (NONMEM), using the software package NONMEM (Version V, Level 1.1 or higher; GloboMax LLC, Hanover, MD).

